#### **4.1.5      Nivolumab or Ipilimumab Dose Modifications**

In the Dose Escalation and Expansion Phase, there will be no nivolumab dose adjustments allowed except for weight changes. Dosing calculations should be based on the body weight assessed at baseline. It is not necessary to re-calculate subsequent doses if the participant weight is within 10% of the weight used to calculate the previous dose. All doses should be rounded up or to the nearest milligram per institutional standard.

In the 1L Nivolumab vs Sorafenib Cohort, all subjects will receive either a flat dose of nivolumab 240 mg IV q2 week or sorafenib 400 mg po BID, and no dose adjustments regardless of weight change are required for nivolumab.

In the Nivolumab plus Ipilimumab Combination Cohort, nivolumab weight based dosing calculations should be based on the body weight assessed at baseline. It is not necessary to

re-calculate subsequent doses if the participant weight is within 10% of the weight used to calculate the previous dose. All doses should be rounded up or to the nearest milligram per institutional standard.

#### **4.1.6 *Nivolumab or Ipilimumab Intrasubject Dose Escalation***

No intrasubject nivolumab or ipilimumab dose escalation will be allowed.

#### **4.1.7 *Nivolumab or Ipilimumab Dose Reductions***

Nivolumab or ipilimumab dose reductions are not permitted in this study.

#### **4.1.8 *Sorafenib Dose Reductions***

For subjects receiving sorafenib in the 1L Nivolumab vs Sorafenib Cohort, if sorafenib dose reduction is required for the management of an adverse event, the sorafenib dose should be reduced to 400 mg daily. Further dose reductions may be done in accordance with the package insert.

#### **4.1.9 *Management Algorithms for Immuno-Oncology Agents***

Immuno-oncology (I-O) agents are associated with adverse events that can differ in severity and duration than adverse events caused by other therapeutic classes. Nivolumab and ipilimumab are considered immuno-oncology agent in this protocol. Early recognition and management of adverse events associated with immuno-oncology agents may mitigate severe toxicity. Management algorithms have been developed to assist investigators in assessing and managing the following groups of adverse events:

- Gastrointestinal
- Renal
- Pulmonary
- Hepatic (see protocol specific updates in [Section 4.1.15](#))
- Endocrinopathies
- Skin
- Neurological

The above algorithms are found in [Appendix 1](#) of this protocol.

#### **4.1.10 *Dose Delay for Nivolumab Monotherapy***

Dose delay criteria apply for all drug-related adverse events. Treatment delay up to 6 weeks (42 days) from the last dose is allowable.

Nivolumab administration should be delayed for the following:

- Any Grade  $\geq 2$  non-skin, drug-related adverse event, with the following exceptions:
  - Grade 2 drug-related fatigue or laboratory abnormalities do not require a treatment delay
- Any Grade 3 skin, drug-related adverse event

- Any Grade 3 drug-related laboratory abnormality, with the following exceptions for asymptomatic amylase or lipase, AST, or ALT:
  - Grade 3 amylase or lipase abnormalities that are not associated with symptoms or clinical manifestations of pancreatitis do not require a dose delay. It is recommended to consult with the BMS Medical Monitor for Grade 3 amylase or lipase abnormalities.
  - If a subject has a baseline AST or ALT that is within normal limits, delay dosing for drug-related Grade  $\geq 2$  toxicity (2-grade shift).
  - If a subject has baseline AST or ALT within the Grade 1 toxicity range, delay dosing for drug-related Grade  $\geq 3$  toxicity (2-grade shift).
  - If a subject has baseline AST or ALT within the Grade 2 toxicity range, delay dosing for drug-related increase in AST or ALT at 2x baseline value or when AST or ALT is 8x ULN (whichever is lower).
- Any adverse event, laboratory abnormality, or intercurrent illness which, in the judgment of the investigator, warrants interrupting the dose of study medication.

Subjects who require delay of nivolumab should be re-evaluated weekly or more frequently if clinically indicated. It is recommended to monitor elevations in AST or ALT approximately every 3 days till levels peak or begin to decline. Nivolumab dosing can be resumed when re-treatment criteria are met.

Tumor assessments for all subjects should continue as per protocol even if study drug dosing is delayed.

#### **4.1.11 Dose Delay for Nivolumab plus Ipilimumab Combination Cohort**

Dose delay criteria apply for all drug-related adverse events. Treatment delay up to 6 weeks (42 days) from the last dose of nivolumab and ipilimumab are allowable in Arms A and B vs 12 weeks (84 days) from the last dose of nivolumab and ipilimumab in Arm C.

Study drug administration should be delayed for the following:

- Any Grade  $\geq 2$  non-skin, drug-related adverse event, with the following exceptions:
  - Grade 2 drug-related fatigue or laboratory abnormalities do not require a treatment delay
- Any Grade 3 skin, drug-related adverse event
- Any Grade 3 drug-related laboratory abnormality, with the following exceptions for lymphopenia, asymptomatic amylase or lipase, AST, or ALT:
  - Grade 3 lymphopenia does not require dose delay.
  - Grade 3 amylase or lipase abnormalities that are not associated with symptoms or clinical manifestations of pancreatitis do not require a dose delay. It is recommended to consult with the BMS Medical Monitor for Grade 3 amylase or lipase abnormalities.
  - If a subject has a baseline AST or ALT that is within normal limits, delay dosing for drug-related Grade  $\geq 2$  toxicity (2-grade shift).

- If a subject has baseline AST or ALT within the Grade 1 toxicity range, delay dosing for drug-related Grade  $\geq 3$  toxicity (2-grade shift).
- If a subject has baseline AST or ALT within the Grade 2 toxicity range, delay dosing for drug-related increase in AST or ALT at 2x baseline value or when AST or ALT is 8x ULN (whichever is lower).
- Any adverse event, laboratory abnormality, or intercurrent illness which, in the judgment of the investigator, warrants interrupting the dose of study medication.

Tumor assessments for all subjects should continue as per protocol even if study drug dosing is delayed.

Subjects receiving ipilimumab in combination with nivolumab that have drug-related toxicities that meet the criteria for dose delay, should have both drugs (ipilimumab and nivolumab) delayed until retreatment criteria are met. Refer to [Section 4.1.17 Criteria to Resume Ipilimumab Dosing](#) for further details.

In subjects in Arm C receiving ipilimumab 1 mg/kg q6week:

- Nivolumab may be delayed until the next planned ipilimumab dose if the next ipilimumab dose is scheduled within the next 12 days. This will permit periodic ipilimumab dosing to be synchronized with nivolumab dosing.
- Ipilimumab should be dosed at the specified interval regardless of any delays in intervening nivolumab doses. However, in order to maintain periodic synchronized dosing of ipilimumab and nivolumab, the dosing days of nivolumab and ipilimumab may be adjusted within the permitted  $\pm 7$ -day window, as long as consecutive nivolumab doses are given at least 12 days apart. Ipilimumab may be delayed beyond the 7-day window if needed to synchronize with the next nivolumab dose.
- If an ipilimumab dose is delayed beyond 6 weeks from the prior ipilimumab dose, then subsequent ipilimumab doses should rescheduled to maintain the 6 week interval between consecutive ipilimumab doses.
- A dose delay of ipilimumab which results in no ipilimumab dosing for  $> 12$  weeks requires ipilimumab discontinuation, with exceptions as noted in [Section 4.2 \(Ipilimumab Dose Discontinuation\)](#).

#### **4.1.12 Treatment Interruption or Discontinuation for Sorafenib**

The decision to interrupt or discontinue sorafenib should follow local standards of care as guided by the locally approved product label or applicable SmPC.

For any dose interruptions, re-initiation of study drugs therapy may be delayed for a maximum of 30 days to allow recovery from any adverse event. In exceptional cases where subjects are responding, re-initiation of therapy after missing  $> 30$  consecutive days of treatment may be done on a case by case basis after confirmation with the BMS medical monitor.

Tumor assessments for all subjects should continue as per protocol even if dosing is delayed.

#### **4.1.13 Treatment Beyond Progression for Sorafenib**

Subjects will be permitted to continue with sorafenib treatment beyond initial RECIST 1.1 defined progressive disease as long as they meet the following criteria:

- Investigator-assessed clinical benefit
- Subject is tolerating sorafenib treatment
- Treatment beyond progression will not delay an imminent intervention to prevent serious complications of disease progression (eg, CNS metastases)
- Subject provides written informed consent prior to receiving any additional sorafenib treatment, using an ICF describing any reasonably foreseeable risks or discomforts, or other alternative treatment options.

The assessment of clinical benefit should take into account whether the subject is clinically deteriorating and unlikely to receive further benefit from continued treatment. The decision to continue treatment beyond initial investigator-assessed progression should be discussed with the BMS Medical Monitor and documented in the study records.

If the decision is taken to continue sorafenib treatment beyond progression, the subject will remain on the trial and continue to be treated and monitored according to the Time and Events Schedule in [Table 5.1-6](#).

Subjects should discontinue study therapy upon further evidence of further progression, defined as an additional 10% or greater increase in tumor burden (SPD: sum of product of diameters) from time of initial progression (including all target lesions and new measurable lesions). New lesions are considered measurable at the time of initial progression if the longest diameter is at least 10 mm (except for pathological lymph nodes, which must have a short axis of at least 15 mm). Any new lesion considered non-measurable at the time of initial progression may become measurable and therefore included in the tumor burden measurement if the longest diameter increases to at least 10 mm (except for pathological lymph nodes, which must have an increase in short axis to at least 15 mm). Sorafenib treatment should be discontinued permanently upon documentation of further progression.

For statistical analyses that include the investigator-assessed progression date, subjects who continue treatment beyond initial investigator-assessed, RECIST 1.1-defined progression will be considered to have investigator-assessed progressive disease at the time of the initial progression event.

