Accumulating evidence indicates that the emergence of objective responses to agents that activate anti-tumor immune responses follows delayed kinetics of weeks or months, and can be preceded by initial apparent radiological progression or the appearance of new lesions or some enlarging lesions while certain target lesions are regressing (“mixed response”). It is thus reasonable, in the absence of clinical deterioration, to continue to treat these subjects until progression is both confirmed and found to have worsened at a subsequent imaging evaluation. Evidence of PD will be based on a comparison with baseline (or nadir) scans or other tumor evaluations. Additional details on treatment beyond progression are located in [Sections 3.1.8](#) (for nivolumab and ipilimumab) and [4.1.13](#) (for sorafenib).

No subject receiving nivolumab or nivolumab plus ipilimumab will be permitted dose escalations or de-escalations. Sorafenib dose adjustments are described in [Section 4.1.8](#) circumstances ([Section 3.1.8](#)). After discontinuation from study therapy, there are 2 follow-up visits required (on site visits), and additional survival follow-up (on-site or phone visits).

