Subjects should discontinue study therapy upon further evidence of further progression, defined as an additional 10% or greater increase in tumor burden SLD from time of initial progression (including all target lesions and new measurable lesions). New lesions are considered measurable if the longest diameter is at least 10 mm (except for pathological lymph nodes, which must have a short axis of at least 15 mm). Any new lesion considered non-measurable may become measurable and therefore included in the tumor burden measurement if the longest diameter increases to at least 10 mm (except for pathological lymph nodes, which must have an increase in short axis to at least 15 mm). Nivolumab treatment should be discontinued permanently upon documentation of further progression.

For statistical analyses that include the investigator-assessed progression date, subjects who continue treatment beyond initial investigator-assessed, RECIST 1.1-defined progression will be considered to have investigator-assessed progressive disease at the time of the initial progression event.

For subjects discontinuing treatment because of global deterioration of health status without objective evidence of disease progression at that time, progression should be reported as “symptomatic deterioration”. Every effort should be made to document objective progression (ie, radiographic confirmation) even after discontinuation of treatment.

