### **3.5 Discontinuation of Subjects from Treatment**

Subjects MUST discontinue investigational product (and noninvestigational product at the discretion of the investigator) for any of the following reasons:

- Withdrawal of informed consent (subject's decision to withdraw for any reason)
- Any clinical adverse event (AE), abnormal laboratory test results or intercurrent illness which, in the opinion of the investigator, indicates that continued participation in the study is not in the best interest of the subject
- Pregnancy, except as described below
- Termination of the study by BMS
- Specific criteria for discontinuation of study drugs outlined for nivolumab in [Section 4.1.18](#), ipilimumab in [Section 4.2](#), or for sorafenib in [Section 4.1.12](#).
- Loss of ability to freely provide consent through imprisonment or involuntary incarceration for treatment of either a psychiatric or physical (eg, infectious disease) illness
- Protocol defined disease progression unless subject is eligible for treatment beyond progression ([Section 3.1.8](#) for nivolumab or ipilimumab and [Section 4.1.13](#) for sorafenib).

In the case of pregnancy, the investigator must immediately notify the BMS Medical Monitor/designee of this event. In most cases, the study drug will be permanently discontinued in an appropriate manner. If the investigator determines a possible favorable benefit/risk ratio that warrants continuation of study drug, a discussion between the investigator and the BMS Medical Monitor/designee must occur.

All subjects who discontinue should comply with protocol specified follow-up procedures as outlined in [Table 5.1-8](#) and [Table 5.1-9](#). The only exception to this requirement is when a subject withdraws consent for all study procedures or loses the ability to consent freely (ie, is imprisoned or involuntarily incarcerated for the treatment of either a psychiatric or physical illness).

If a subject was withdrawn before completing the study, the reason for withdrawal must be entered on the appropriate case report form (CRF) page.

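### In the randomized 1L cohort, the permanent-stop rule after progression is a 10% rise in SPD on sorafenib but a 10% rise in SLD on nivolumab, with no reason given

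*Combined protocol and SAP*

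**What the plan says.** Section 4.1.13 covers sorafenib after initial progression. Treatment must end at further progression, "defined as an additional 10% or greater increase in tumor burden (SPD: sum of product of diameters) from time of initial progression", and "Sorafenib treatment should be discontinued permanently upon documentation of further progression". Section 3.1.8 covers nivolumab. There the trigger is "an additional 10% or greater increase in tumor burden SLD from time of initial progression", with the same consequence: "Nivolumab treatment should be discontinued permanently upon documentation of further progression".

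Both rules operate inside one cohort of about 130 subjects randomized 1:1 (Section 3.1). Section 3.1.1, Treatment Phase ("Additional details on treatment beyond progression are located in"), names 3.1.8 for nivolumab and ipilimumab and 4.1.13 for sorafenib. Section 3.5 makes the same split where it lists the stop for "Protocol defined disease progression unless subject is eligible for treatment beyond progression".

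The two sections otherwise nearly match. They share the entry conditions (clinical benefit, tolerance, no delay to an imminent intervention, written consent, Medical Monitor discussion), the lesion set (target plus new measurable lesions) and the 10 mm and 15 mm measurability limits. In 4.1.13, as in 3.1.8, measurability rests on a single diameter: "New lesions are considered measurable at the time of initial progression if the longest diameter is at least 10 mm", with a short-axis limit for nodes. Both state that subjects treated beyond progression "will be considered to have investigator-assessed progressive disease at the time of the initial progression event".

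**The concern.** SPD is an area measure and SLD a length measure, so 10% of one is not 10% of the other. With near-identical wording around them, the two rules look equivalent but are not. Section 3.1.8 explains why treatment beyond progression is allowed, but not the choice of measure. Section 4.1.13 gives no rationale. Section 1.1.6 justifies handling the arms differently only for recognising and managing adverse events.

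SPD also fits this cohort badly. Section 3.3.2.1 (item 2.d) requires a lesion measurable in one dimension under RECIST 1.1, whereas SPD needs a second diameter for every lesion.

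The stop rule governs several things that can then differ by arm for the same tumour course:

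- exposure after progression;
- the adverse-event window, which runs at least 100 days from last dose (Section 3.1.1, Follow Up Phase);
- how long 1L scans continue, since they run to the later of progression or treatment discontinuation (Section 3.1.1, Treatment Phase);
- the timing of later therapy, which bears on OS, a secondary objective of this cohort (Section 1.3.2).

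**Working it through.** The plan gives no figure to reproduce. The check converts one threshold into the other.

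**From the protocol:** the 10% threshold in both arms; SPD (4.1.13) versus SLD (3.1.8); 1L scans every 8 weeks (56 days) for the first 48 weeks (3.1.1); nivolumab every 2 weeks; new lesions measurable from 10 mm. **Assumed:** all lesion sizes, round shape, growth patterns and growth rates.

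**1. All lesions grow by the same fraction g in both diameters.** SLD rises by g and SPD by (1+g)² − 1.

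- Sorafenib stops at g = √1.10 − 1 = 4.88%.
- Nivolumab stops at g = 10%, where SPD has risen 1.10² − 1 = 21%.
- With diameter d₀·exp(rt), the times are ln(1.10)/(2r) and ln(1.10)/r. Sorafenib reaches its threshold in half the time at any rate.

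To read this at scans, use volume doubling time T = t·ln 2 / (3·ln(1+g)) with t = 56 days. For g = 10%, T = 135.8 days; for g = 4.88%, T = 271.5 days.

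- T up to 136 days: both thresholds are met at the first 8-week scan, so there is no difference.
- T from 136 to 272 days: SPD is met at day 56 and SLD at day 112. The gap is one scan, or 8/2 = 4 nivolumab doses.
- T above 272 days: the SPD time exceeds 56 days and the SLD time is twice as long, so the stops are at least one scan apart.

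This ignores the ±1 week window and the change to 12-week scans after week 48.

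**2. Only one of two round lesions (60 mm and 10 mm) grows.** SLD = 70; SPD = 3600 + 100 = 3700, so the SPD trigger is 1.1 × 3700 = 4070.

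| Growing lesion | Growth at SLD trigger | Growth at SPD trigger | Stops first |
|---|---|---|---|
| 60 mm | 7/60 = 11.7% | √(4070 − 100)/60 − 1 = 5.0% | sorafenib |
| 10 mm | 7/10 = 70% | √(4070 − 3600)/10 − 1 = 116.8% | nivolumab |

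Beside an unchanged 60 mm lesion, the order switches where 0.1(60+b)/b = √(1.1 + 360/b²) − 1. This gives b ≈ 20.9 mm.

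**3. A new 10 mm lesion appears beside n equal round lesions of diameter D.** SLD rises by 10/(nD), which is at least 10% if D ≤ 100/n. SPD rises by 100/(nD²), which is at least 10% if D ≤ √(1000/n). Nivolumab stops and sorafenib does not when D lies between the two limits:

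| n | D (mm) |
|---|---|
| 1 | 31.6 to 100 |
| 2 | 22.4 to 50 |
| 5 | 14.1 to 20 |

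Outside these ranges the two rules agree. Example with n = 2, D = 40 mm: SLD +10/80 = 12.5%; SPD +100/3200 = 3.1%.

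**The case against.** The two sections govern different drugs, and a site can follow both as written, so this is an unexplained asymmetry rather than a strict contradiction. It might even be intended: 3.1.8 rests on immune-specific reasons for late response that do not apply to sorafenib, and a tighter sorafenib rule would fit that. The consequences are modest. Progression dates are fixed at the initial event, Amendment 14 made the 1L efficacy analysis one of estimation, and exposure already differs because only sorafenib allows dose reduction. Continuation is also limited by clinical judgement, consent and Medical Monitor discussion. The sizes above are hypothetical, their direction reverses, and a change now would put sorafenib subjects under two rules.

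Much of this stands, and it limits the severity. No net bias and no effect on a reported estimate is shown, and the number of subjects affected is unknown. The appeal to intent does not carry the point. No section cited here states such an intent, and SPD is not the tighter measure in every growth pattern, so it would not reliably serve one. Nor does that explain a measure needing a second diameter in a cohort whose lesions are assessed in one dimension. A clarification letter could confirm what was meant, but it would leave the differing stop rules in force.

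**Conclusion.** The concern holds. Two arms of one randomized cohort have permanent-stop rules with the same percentage on different measures, and none of the four sections cited explains it. Under uniform growth the thresholds are 4.9% and 10% in diameter. Under growth confined to small or new lesions the order can reverse. These sizes rest on assumed lesion sizes, shapes and growth.

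What is exposed is arm-dependent time on treatment after progression and what follows from it. Investigator-assessed TTP and PFS dates are not affected, and no formal test is at risk. Severity is low to moderate, but the text should be changed.

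One limit: the text available for this check ended within the Section 5.1 schedules. Section 5.4, Table 5.1-6, Section 8 and the RECIST appendices could not be searched for a reason.

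**What to change.** In Section 4.1.13, replace SPD and its expansion with SLD, as in Section 3.1.8. Under uniform growth this moves the sorafenib stop from +4.9% to +10% in diameter. Notify sites, and apply the change from activation of the amendment onward. Accrual to this cohort was to begin on activation of Amendment 8 (dated 31-Jul-2015) and the current protocol is dated 26-Oct-2016, so some sorafenib subjects may already have been managed under SPD. Identify them in reporting, because the cohort will then contain sorafenib subjects under two rules.

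The cost is one phrase in an amendment needing IRB/IEC approval (Section 2.1), a site notice, and possibly a site query to find those subjects. No new scans are needed, because SLD uses the diameters already measured for RECIST 1.1. If SPD was in fact intended, Section 4.1.13 should give the reason.
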